#### **7.5 Other Safety Measures**

Data for COVID-19 clinical features will be listed and tabulated.

Data for hospital interventions will be listed and summarized by presenting frequency counts and percentages for each category. The duration (number of days) of inotropes/vasopressors administration will be calculated based on the start/stop dates recorded on the eCRF and summarized descriptively. Subjects who were never on inotropes/vasopressors will be included in the descriptive summary with a value of zero days of duration.

### **8. INTERIM ANALYSES**

#### **8.1 Interim Safety Analysis**

An interim analysis will be conducted after 50 subjects (approximately 25 per group) for safety variables through Day 29. Due to the exploratory nature of this phase 2 study, the multiplicity adjustments will not be considered. This interim evaluation simply represents Sponsor safety due diligence. This interim analysis will analyze safety variables including, but not limited to, the following: adverse events (see Section 7.2), clinical laboratory parameters (see Section 7.3), and vital signs (see Section 7.4). The relevant methods described in Section 7 (Safety Analysis) of this SAP intended for the final analysis will also be applicable to the interim analysis.

#### **8.2 Interim Futility Analysis**

An interim futility analysis will be conducted based on all available data assessable for the primary endpoint and key secondary efficacy endpoints to assess whether the trial will be terminated due to lack of efficacy (futility). The unblinded output will be reviewed by an independent unblinded team, and the study team will remain blinded. Determination of futility from the interim futility analysis will be based on the conditional power (the power conditional on the observed data accumulated at the interim analysis) for the primary outcome, as well as assessment of the secondary efficacy outcomes.

The futility analysis will include for the primary efficacy endpoint variable, all patients with data

through Day 29, and for the following secondary efficacy endpoint variables, all patients with data through Day 29, as specified for each endpoint:

- Assessment of Clinical Severity: Change in NEWS from baseline (Day 1 through Day 29)
- Time to clinical response: NEWS  $\leq 2$  maintained for 24 hours, Day 1 through Day 29
- Time to hospital discharge: defined as duration of hospitalization from Day 1 through Day 29 (and duration of hospitalization)
- If admitted to ICU post randomization: Duration of ICU stay through Day 29
- Duration of any oxygen use Day 1 through Day 29
- If requiring mechanical ventilation post randomization: Duration mechanical ventilation through Day 29
- Absolute value and mean change from baseline in the Ordinal scale Day 1 through Day 29
  - The Ordinal scale is as follows:
    - 1) Death;
    - 2) Hospitalized, on invasive mechanical ventilation or extracorporeal membrane oxygenation (ECMO);
    - 3) Hospitalized, on non-invasive ventilation or high flow oxygen devices;
    - 4) Hospitalized, requiring supplemental oxygen;
    - 5) Hospitalized, not requiring supplemental oxygen;
    - 6) Not hospitalized, limitation on activities;
    - 7) Not hospitalized, no limitations on activities.
- Proportion (percentage) of subjects in each severity category of the 7-point Ordinal scale at Day 15 and Day 29
- Time to sustained normalization of temperature and proportion of subjects with normalization of fever at all time points, defined as temperature  $< 36.6^{\circ}\text{C}$  armpit,  $< 37.2^{\circ}\text{C}$  oral, or  $< 37.8^{\circ}\text{C}$  rectal sustained for at least 24 hours
- Number of subjects who develop Acute Respiratory Distress Syndrome (ARDS) through Day 29
- Length of time to clinical progression through Day 29 (defined as the time to death, mechanical ventilation, or ICU admission)

If the results of the interim futility analysis are not promising, the trial may be terminated. Otherwise the study will continue as originally planned unless discontinued for business or feasibility reasons.

The futility analysis will not inflate the type I error since the trial will not be stopped to claim efficacy. The primary and key secondary efficacy outcomes will be analyzed using the methods described above in Section 6.1 and 6.2. No subgroup or sensitivity analyses are planned for the futility analysis.

Suppose at the time of data-cut for the futility analysis,  $x_0$  subjects meet the primary efficacy endpoint among  $m_0$  subjects in the placebo group, and  $x_1$  subjects have events among  $m_1$  subjects in the active (Alpha1-PI) group. Let  $\tilde{p}_g = x_g/m_g$  for group  $g = 0, 1$ ; and  $\tilde{p} = (x_0 + x_1)/(m_0 + m_1)$ .  $Z_1 = \frac{\tilde{p}_1 - \tilde{p}_0}{\sqrt{(\tilde{p}_0^{-1} + \tilde{p}_1^{-1})\tilde{p}(1-\tilde{p})}}$  is the z-score corresponding to the Chi-square statistic.

Let the final sample size be  $n_0$  and  $n_1$  in the placebo and active (Alpha1-PI) groups respectively. Let  $Z_{1-\alpha/2}$  be the  $1 - \alpha/2 = 97.5\%$  percentile of the normal distribution, which can be calculated as the PROBIT function in SAS. Let  $t = (n_0^{-1} + n_1^{-1})/(m_0^{-1} + m_1^{-1})$ . The conditional power (CP) for the primary efficacy endpoint (active compares to placebo group) will be calculated using the formula:

$$CP = 1 - \Phi \left( \frac{Z_{1-\alpha/2} + Z_1/\sqrt{t}}{\sqrt{1-t}} \right)$$

where  $\Phi$  is the cumulative distribution function (CDF) for  $N(0,1)$ .

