## 4. GENERAL CONSIDERATIONS FOR DATA ANALYSIS

Unless otherwise specified, continuous variables will be summarized using descriptive statistics

(n, mean, standard deviation, median, minimum, and maximum). Categorical variables will be summarized showing the number and percentage of subjects within each category.

Summary results will be provided for each treatment group. All tabulations will be based on pooled data across centers.

All statistical tests will be two-sided and tested at the 5% level of significance.

Analyses will be performed using SAS for Windows statistical software, version 9.4 or higher (SAS, Cary, NC), except where other software may be deemed more appropriate. In the event that other software is used to perform some analyses, the details will be provided in the Clinical Study Report.

██████████ will perform all efficacy and safety analyses described in this SAP and Grifols will review them.

Subject data will be listed, sorted by treatment group and subject number. When applicable, listings will be additionally sorted by visit and assessment date/time.

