#### **4.1 Data Quality Assurance**

Once all the source verification is complete, all queries are resolved, and the database has been updated appropriately, the database will be locked and made available to █████ Biostatistics for final analysis.

Data may be pulled by █████ Biostatistics for interim analyses at a time when source verification and query resolution is ongoing.

All SAS programs used to create analysis data sets, tables, and listings are double programmed. The SAS outputs will be compared and the programs will be updated until the outputs match.

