### 6.1 Primary Efficacy Endpoint and Analysis

The primary efficacy analysis will be carried out on the ITT population. If there is difference between the PP population and ITT population, the analysis will be repeated using the PP population.

The primary efficacy variable is the proportion of subjects who die or require ICU admission on

or before Day 29, or who are dependent on high flow oxygen devices or invasive mechanical ventilation on Day 29. The primary efficacy endpoint will be derived based on the subject status (Alive/Death), ICU admission, mechanical ventilation and oxygen administration recorded in the database. Subjects who met any of the criteria listed below will be treated as meeting the primary efficacy endpoint:

- 1) Death is recorded on the eCRF All Visits page “General Duration of Hospitalization, & Overall Requirement for Mechanical Ventilation, ICU Admission and/or Oxygen Supplementation”;
- 2) ICU admission date is recorded on the eCRF All Visits page “General Duration of Hospitalization, & Overall Requirement for Mechanical Ventilation, ICU Admission and/or Oxygen Supplementation”;
- 3) On the eCRF Day 29 page “Mechanical Ventilation and Oxygen Administration”:
  - a. subject on mechanical ventilation is recorded in the mechanical ventilation record for that day, i.e., “Is the subject on a ventilator?” is recorded as “Yes”;
  - Or
  - b. the modality of oxygen administration is recorded as “High flow oxygen devices”

If for a subject any of the 4 criteria above could not be assessed due to missing data, then the subject will be treated as meeting the endpoint in the primary efficacy analysis.

The null hypothesis is that there is no difference in the proportions of subjects who met the primary endpoint between randomized groups;  $H_0: \pi_t - \pi_c = 0$ . The alternative hypothesis is that the proportions of subjects who met the primary endpoint are different between the treatment groups;  $H_1: \pi_t - \pi_c \neq 0$ .

The proportion of subjects who met the criteria for the primary endpoint within each treatment group will be presented along with a two-sided exact (Clopper-Pearson) 95% confidence interval (CI).

The observed difference in the proportion of subjects meeting the criteria between treatment groups along with the exact unconditional 95% CI for risk difference will be calculated. The null hypothesis will be tested using Chi-square statistic and the p-value will be reported.

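### SAP 8.2 builds the interim z-score from inverse event proportions instead of inverse sample sizes; coded as it reads, the futility conditional power stays near zero whatever the data show

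*SAP*

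**What the plan says.** SAP Section 8.2 sets the group event proportion as p~g = xg/mg, where xg is the number of subjects meeting the primary endpoint and mg the number of subjects in the group at the data cut, and takes p~ as the pooled proportion. Z1 is p~1 - p~0 divided by a square root that reads, in the supplied text, (1/p~0 + 1/p~1) p~(1 - p~). The SAP describes the result this way: "p}_0^{-1} + \tilde{p}_1^{-1})\tilde{p}(1-\tilde{p})}}$ is the z-score corresponding to the Chi-square statistic".

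A few lines later the information fraction is written with inverse sample sizes: "t = (n_0^{-1} + n_1^{-1})/(m_0^{-1} + m_1^{-1"). CP is then 1 - Φ((1.96 + Z1/√t)/√(1 - t)), so the interim event counts enter only through Z1.

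CP for the primary outcome is one basis for the futility judgement, "as well as assessment of the secondary efficacy outcomes". At the same look, "The primary and key secondary efficacy outcomes will be analyzed using the methods described above in Section 6.1 and 6.2". For the primary endpoint Section 6.1 specifies: "The null hypothesis will be tested using Chi-square statistic and the p-value will be reported". No numerical CP threshold is set. The trial may be stopped if the results are judged not promising. Protocol Section 9.3 names conditional power but gives no formula, so SAP 8.2 is its only specification.

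**The concern.** A z-score for a difference in proportions divides by a standard error, which must shrink as the groups grow. The denominator as written contains no sample size, so Z1 is the same for 25 or 50 subjects per arm at the same event rates. It also cannot be computed when either arm has no events.

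The sentence and the formula therefore specify different quantities. If the program follows the formula, a strong interim benefit and a null result both give a CP close to zero. The error pushes towards stopping a trial that is doing well, and a wrongful stop could not be undone.

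**Working it through.** **Inputs from the documents.** Two-sided 5% tests (SAP 4), hence a critical value of 1.96 in the CP formula. Uncorrected chi-square as the primary test (SAP 6.1 mentions no continuity correction). About 100 subjects randomized 1:1 (SAP 3.1 and 9), taken as n0 = n1 = 50.

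**Assumptions.** The size of the futility cut and the event rates are not stated. The main illustration uses m0 = m1 = 25, the approximate size of the safety interim, so t = (2/50)/(2/25) = 0.5. Other cuts follow below. The SAP states no CP value to reproduce, so the check is against its own verbal definition of Z1.

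**Worked example: placebo 8/25, active 2/25.** Here p~0 = 0.32, p~1 = 0.08, p~ = 10/50 = 0.20 and p~(1 - p~) = 0.16.

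- With inverse sample sizes: √((1/25 + 1/25) × 0.16) = √0.0128 = 0.1131, so Z1 = -0.24/0.1131 = -2.12. Its square is 4.50, which equals the Pearson chi-square (p = 0.034).
- As written: √((1/0.32 + 1/0.08) × 0.16) = √(15.625 × 0.16) = √2.5 = 1.581, so Z1 = -0.24/1.581 = -0.15. Its square is 0.023, not 4.50.

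**Dependence on sample size.** At 16/50 against 4/50 the proportions are the same. The chi-square z-score moves to -3.00, and Z1 as written stays at -0.15.

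**Conditional power at t = 0.5.**

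- Correct: (1.96 - 2.12/0.7071)/0.7071 = -1.47, so CP = 93%.
- As written: (1.96 - 0.152/0.7071)/0.7071 = 2.47, so CP = 0.7%.

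| Placebo v active, of 25 | Correct Z1 | Correct CP | Z1 as written | CP as written |
|---|---|---|---|---|
| 8 v 8 | 0 | 0.3% | 0 | 0.3% |
| 8 v 4 | -1.32 | 45% | -0.12 | 0.6% |
| 10 v 5 | -1.54 | 62% | -0.16 | 0.7% |
| 8 v 2 | -2.12 | 93% | -0.15 | 0.7% |
| 12 v 3 | -2.78 | 99.7% | -0.24 | 1.1% |

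**All tables with 1 to 12 events per arm at 25 per arm (144 tables).** CP as written runs from 0.06% to 1.1%. In the 22 tables where correct CP is 80% or more, it runs from 0.5% to 1.1%.

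**Other cuts.** Largest CP as written, with the correct CP for the same table, event rates capped at 50%:

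| Per arm at cut | Table | CP as written | Correct CP |
|---|---|---|---|
| 15 | 7 v 2 | 3.4% | 97.7% |
| 20 | 10 v 3 | 2.2% | 98.9% |
| 25 | 12 v 3 | 1.1% | 99.7% |
| 30 | 15 v 4 | 0.5% | 99.9% |

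Raising the cap to 60% gives maxima of 5.0%, 3.1%, 1.7% and 0.7%. With no cap at 25 per arm, the maximum is 8.7%, at 25/25 against 8/25.

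**Zero events.** With no active-arm events in 25, Z1 as written divides by zero. The chance of this is 0.9^25 = 7% at an assumed true rate of 10%, and 0.95^25 = 28% at 5%.

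**The rest of the formula.** The fraction t is right, and the sign suits an endpoint where fewer events is better. A simulation of the current-trend model at Z1 = -1.333 and t = 0.5 gave 45.7%, against 45.8% from the formula. The fault is confined to one term.

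**The case against.** The strongest point is provenance. The finding rests on one symbol in a nested, machine-read formula, and the supplied text shows the reader making errors elsewhere: the product name is garbled in some page headers, and the compliance formula in SAP 7.1 has unbalanced brackets. An m could have been read as p~. This stands as a reason to check the original page. It does not settle the matter, because the inverse sample sizes came through intact in t in the same section.

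Second, the SAP names the intended quantity, and a statistician told to compute the chi-square z-score would know how. That is fair, and the harm arises only if the formula is coded literally. But when words and formula differ, the plan does not say which governs.

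Third, there are safeguards. The Section 6.1 p-value would be produced at the same look, and p = 0.034 beside CP of 0.7% ought to raise a question. A zero-event arm would fail visibly. SAP 4.1 adds: "All SAS programs used to create analysis data sets, tables, and listings are double programmed". The first two may help, but no step requires the p-value and CP to be compared. Double programming checks that two programs agree, and two programs following the same formula will agree.

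Fourth, CP as written largely keeps the order of the tables (Spearman correlation with correct CP 0.98 over the 144). It does carry rank information, but conditional power is read as a probability, and on that scale nothing looks promising.

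Finally, no CP threshold is set and the secondary outcomes are weighed too, so the effect on the stopping decision cannot be quantified. That limits the claim about consequences, not the claim that the formula is wrong.

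**Conclusion.** The concern holds on the supplied text. Z1 as written is not the chi-square z-score, and CP computed from it stays close to zero for any plausible interim result. At an assumed cut of 25 of 50 per arm, a result with correct CP of 93% would be reported as 0.7%. The conclusion holds at every cut examined from 15 to 30 per arm, where CP as written never exceeds 5.0% with event rates up to 60%.

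It rests on two conditions: that the symbol is the same in the original SAP, and that the program follows it. Confidence is medium for that reason. It should be fixed before the futility look. The type I error of the final analysis is not affected.

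**What to change.** Confirm the symbol against the original SAP page. If it is as supplied, replace the denominator of Z1 in Section 8.2 with √((1/m0 + 1/m1) p~(1 - p~)).

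Whatever the page shows, run the program before unblinding on one test case: placebo 8/25, active 2/25, 50 per arm at the final analysis. It should return Z1 = -2.12 and CP = 93%.

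The cost is one corrected term in the SAP and one program check. No protocol amendment and no additional subjects are needed.

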## 9. SAMPLE SIZE AND POWER CALCULATIONS

Because of the urgency and lack of previous prospective COVID-19 data, sample size estimation remains incompletely defined; however, the size of this pilot study is commensurate with other Phase 2 investigations ongoing during the COVID-19 pandemic. Approximately 100 subjects are allowed to be randomized as part of a humanitarian effort against COVID-19.

## 11. APPENDIX

### 11.1 Appendix A: Schedule of Events

Study Period	Screen/ Baseline	IP	SMT and Daily Evaluations 										Follow-Up	Follow-Up Clinic Visit Day			
			2	3	4	5±1 m day	6	7	8	9	10	11-14 Daily if in hospital	15± 1 day m	16-28 Daily if in hospital	29 a ± 1 day m	Day 60 ± 2 days	Day 90 ± 2 days
Study Day Procedures/assessments	1	1 st IP infusion day															
Informed consent	X																
Inclusion/exclusion criteria	X																
Demography, (including age [year of birth], gender, race, and ethnicity), disease characteristics (date of exposure, date of onset a )	X																
Pregnancy test b	X																
Ordinal Scale (at the 1 st assessment of a given day) c	X		X	X	X	X	X	X	X	X	X	X	X	X	X		
National Early Warning Score (NEWS) (Appendix 2)	X		X	X	X	X	X	X	X	X	X	X	X	X	X		
Clinical features key symptoms: fever, cough, shortness of breath, fatigue, myalgia etc.	X		X	X	X	X	X	X	X	X	X	X	X	X	X		
Vital signs (temperature, systolic and diastolic blood pressure, pulse, respiratory rate)	X	X i	X	X	X	X	X	X	X i	X	X	X	X	X	X		
Weight	X																
Record result of historical SARS-CoV-2 PCR (qualitative RT-PCR) or NAT or other commercial or public health assay approved by regulatory authorities as a diagnostic test for COVID-19 in any specimen during the current hospital admission OR 96 hours prior to the hospital admission date and prior to randomization (the SARS-CoV-2 test results must be performed by a hospital laboratory and the documentation available) (eligibility criterion)		X															

## Schedule of Events (Continued)

Study Period	Screen/ Baseline	IP	SMT and Daily Evaluations l										Follow-Up	Follow-Up Clinic Visit Day				
			2	3	4	5±1 m day	6	7	8	9	10	11-14 Daily if in hospital	15± 1 day m	16-28 Daily if in hospital	29 e ± 1 day m	Day 60 ± 2 days	Day 90 ± 2 days	
Study Day Procedures/assessments	1	1 st IP infusion day																
Record any supplemental oxygen administration (type, %, flow start/end date/time)	X		X	X	X	X	X	X	X	X	X	X	X	X	X			
If subject requires mechanical ventilation post randomization: Record any mechanical ventilation (start/end date/time)			X	X	X	X	X	X	X	X	X	X	X	X	X			
Record oxygen saturation (specify on or off oxygen supplementation)	X		X	X	X	X	X	X	X	X	X	X	X	X	X			
Randomization ( after all Screen/Baseline assessments complete )	X																	
IV dose of blinded Liquid Alpha-PI (Human) 120 mg/kg body weight (or Placebo) given on Day 1 and Day 8		X								X k								
Record hospital admission and discharge dates	X														X f			
If subject requires ICU admission post randomization: Record ICU admission & discharge dates															X f			
Assessment of ARDS (Berlin Criteria) (Appendix 3)	X					X						X		X				
Respiratory sample for quantitative measurement of SARS-CoV-2 viral load by NAT or PCR (real-time RT-PCR) (obtained via nasopharyngeal swab)	Pre randomized treatment g					X						X		X				
Sample for quantitative measurement of IgM and IgG antibodies to SARS-CoV-2 (if antibodies cannot be determined quantitatively store serum samples frozen at -70°C for later analysis at an external lab)	Pre randomized treatment g					X						X		X				

## Schedule of Events (Continued)

Study Period	Screen/ Baseline	IP	SMT and Daily Evaluations 									Follow-Up	Follow-Up Clinic Visit Day				
			2	3	4	5±1 m day	6	7	8	9	10		11-14 Daily if in hospital	15± 1 day m	16-28 Daily if in hospital	29 a ± 1 day m	Day 60 ± 2 days
Study Day Procedures/assessments	1	1 st IP infusion day				X						X		X			
Serum Chemistry (creatinine, albumin, alanine aminotransferase [ALT], total bilirubin, lactate dehydrogenase [LDH])	Pre randomized treatment g					X						X		X			
Calculate an estimated glomerular filtration rate (eGFR) using the Cockcroft-Gault formula	Pre randomized treatment g					X						X		X			
Ferritin, CRP, D-dimer	Pre randomized treatment g					X						X		X			
Hematology & absolute neutrophil & lymphocyte count (hemoglobin, hematocrit, platelet count, leukocyte count with differential)	Pre randomized treatment g					X						X		X			
Cytokine panel h	Pre randomized treatment g					X						X		X			
Levels of alpha 1-PI (AAT) activity and antigen (both plasma [sodium citrate] and serum samples to be stored for measurement of both antigenic content and functional activity [potency])	Pre randomized treatment g											X ej					
Record SAEs and TEAEs d	X	X	X	X	X	X	X	X	X	X	X	X	X	X	X		
Record standard care concomitant medications	X	X	X	X	X	X	X	X	X	X	X	X	X	X	X		
Phone Checks for Vital Status (living or deceased), any hospital re-admissions or SAEs/non-serious AEs after Day 29 Final Clinic Visit															X	X	

a Date of first contact with the virus, date of first symptoms, date of PCR (RT-PCR)/NAT positive

b Human chorionic gonadotropin-based assay for women of childbearing potential (urine matrix is also valid).

c Ordinal scale measure of clinical status: 1) Death; 2) Hospitalized, on invasive mechanical ventilation or ECMO; 3) Hospitalized, on non-invasive ventilation or high flow oxygen devices; 4) Hospitalized, requiring supplemental oxygen; 5) Hospitalized, not requiring supplemental oxygen; 6) Not hospitalized, limitation on activities; 7) Not hospitalized, no limitations on activities.

- d Grade 3-5 TEAEs will be defined according to CTCAE criteria, US Department of Health and Human Services, NIH, and NCI. In this clinical study, disease progression is defined as the worsening of a subject's condition attributable to the disease for which the investigational product is being studied. It may be an increase in the severity of the targeted disease and/or increases in the symptoms of the targeted disease. Anticipated symptoms of COVID-19 include fever, cough, hypoxia, dyspnea, hemoptysis, myalgia, fatigue, pharyngitis, which may develop at any time during the course of the disease. The development of COVID-19 symptoms during the clinical study should not be recorded as individual TEAEs, unless there is evidence suggesting a causal relationship between blinded Liquid Alpha1-PI (Human)/Placebo and the TEAE.
- e Final Clinic Visit, followed by Phone Checks.
- f Record hospital and ICU discharge date on or before Day 29/Final Visit.
- g All laboratory tests and serum and plasma samples must be obtained from all subjects; samples must be obtained prior to the blinded Liquid Alpha1-PI (Human) infusion on Day 1 and Day 8. (Day 8 AAT levels only apply if second infusion given)
- h Cytokine panel includes IL-1 $\beta$ , IL-10, IL-6, IL-8 IL-2, interferon  $\gamma$ , and TNF- $\alpha$ . Note: serum samples must be stored at -70° C for later analysis at a reference laboratory.
- i. During study infusions on Day 1 and Day 8 vital signs will be measured immediately before the start of infusion, after the first 5 minutes of infusion, and subsequently at 5-10 minute intervals during infusion until the end of infusion. Vital signs will also be measured 2 hours after the end of study infusion.
- j. Day 8 AAT measurement for activity and antigen is only required if subject is in hospital.
- k. If the patient has been discharged from the hospital at the time of the Day 8 blinded Liquid Alpha1-PI (Human) or Placebo infusion, the 2nd infusion is not mandatory, and is at the discretion of the Principal Investigator and subject
- l. Only applicable if subject remains hospitalized, except for Day 5 when all assessments are mandatory for all subjects.
- m. Mandatory even if subject has been discharged from hospital

Note: For assessment for early withdrawal see Section 5.3.4.

